### 8.2.2 Dose Modification for Hepatotoxicity, Nausea/Emesis, and Hyperglycemia

**Hepatotoxicity** – Turalio® and Sirolimus should be discontinued if hepatotoxicity is observed as detailed in Tables 5 and 6.

Reductions or interruptions of the Turalio® dose for toxicity may take place at any time during the study according to the guidelines in [Tables 5 and 6](#). Dose reduction/interruption guidelines for hematologic and nonhematologic treatment-related TEAEs are based on severity. Dose interruptions can be implemented at the discretion of the treating Investigator to manage intolerable or clinically significant toxicity. Interruptions due to toxicity lasting  $>$  21 d require treatment discontinuation unless the medical monitor approves continuation.

**Nausea and Vomiting** – Turalio® may be associated with nausea and/or emesis that can arise early in the course of therapy. Sirolimus may also contribute to nausea and emesis and may be held as well at the discretion of the treating physician.

| Nausea and Vomiting |   |
|----------------------------|---|
| Grade 3                    | Hold Turalio® and Sirolimus dosing until improved to grade 1 or baseline. If improvement of symptoms in less than 48 hours from start of maximal supportive treatment, then restart at 400mg orally in AM and 400mg orally in PM daily.

If symptoms do not improve within 48 hours despite maximal supportive treatment, hold Turalio® and Sirolimus, and consult with Principal Investigator. |
| Grade 4                    | If grade 4 toxicity despite maximal supportive treatment, hold Turalio® and Sirolimus, and consult with Principal Investigator.   |

**Table 12.** Nausea and emesis dose modification recommendations

**Hyperglycemia** – immunosuppressive agents, including Sirolimus have been associated with hyperglycemia that responds to treatment.

| Hyperglycemia – Assessed by Fasting Blood Glucose              |   |
|---|---|
| Grade 1 = > ULN - 160 mg/dL   | Maintain Turalio® and Sirolimus dosing and institute diet modifications. Address any underlying contributing factors (infection, steroids) and consider initiating blood glucose lowering therapy.  |
| Grade 2 = > 160 - 250 mg/dL   | Maintain Turalio® and Sirolimus dosing and initiate blood glucose lowering therapy.   |
| Grade 3 = > 250-500 mg/dL

OR

Hospitalization indicated. | Hold only Sirolimus and initiate blood glucose lowering therapy. Reinstitute Sirolimus if $\leq$ Grade 2.

• If $\leq$ 7 days, dose reduction is at discretion of treating physician.

• If $>$ 7 days, dose reduce to 1mg orally daily if study related. |
| Grade 4 = > 500 mg/dL

OR

Life threatening consequences. | Discontinue from study drug treatment if AE considered study related.   |

**Table 13.** Hyperglycemia dose modification recommendations

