### **8. DOSING DELAYS/DOSE MODIFICATIONS**

#### **8.1 Phase 1 Dose Modification**

All patients may have dose modifications at any time. During Cycle 1 in the phase 1 portion, however, the DLT must be recorded for safety purposes prior to dose reduction. Patients may have drug held for any reason for up to 14 days before discontinuing study treatment. Refer to Tables 4 - 7 below for specific dose modification instructions.

Patients will undergo therapeutic monitoring with trough levels of Sirolimus on day 2 of cycle 1 before receiving daily dose of Sirolimus on day 2 (+2 day window), day 8, day 15, and day 22 of Cycle 1, on day 1 of each subsequent cycle, unless clinically indicated, and during the End-of-Study visit. Trough levels may be measured at other time points as clinically indicated. As levels  $>18.0\mu\text{g}/\text{L}$  are more likely to be associated with an adverse events, dosing of Sirolimus will be held and/or reduced in the case of trough levels  $>18.0\mu\text{g}/\text{L}$  as indicated in the dose modification table (Table 4). Deviation of this dose modification can be done at the discretion of the treating investigator in discussion with the study principal investigator.

| Sirolimus Monitoring and Dose Modification |   |
|---|---|

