Toxicities that occur outside the DLT window will be taken into consideration when determining the RP2D. Reduction/interruption of dosing for AEs may take place at any time. Below are guidelines for dosage modification for Turalio®-related toxicities as well as guidelines for their management. Dose reductions should occur in increments of 200 mg/day, depending on the toxicity grade, as noted in Table 9. These parameters are only a guide and are not intended to supersede the clinical judgment of the treating physician. All adjustments should be made in consultation with the principal investigator. Dosing interruptions longer than three weeks for any reason should generally result in discontinuation from the study, unless the patient has demonstrated a clinical benefit from therapy and would like to continue dosing with study drug after discussion between the investigator and the Sponsor.

| Toxicity Grade
(CTCAE v4)  | Turalio® and
Sirolimus dose changes
during current
treatment period   | Dose adjustments for resumption of treatment   |
|---|--|---|
| Hematologic Toxicity   |  |   |
| Any Grade 4, or Grade 3 neutropenia with fever, or thrombocytopenia with bleeding and except for Grade 4 lymphopenia |  |   |
| 1 st Appearance  | Interrupt until ANC recovers to $\geq 1 \times 10^9/L$ ; growth factor support permitted | Dose reduce one dose level. If dose level 1 at time of AE, discontinue both drugs.            |
| 2 nd Appearance  | Interrupt until ANC recovers to $\geq 1 \times 10^9/L$ ; provide growth factor support   | Dose reduce one additional dose level. If dose level 1 at time of AE, discontinue both drugs. |
| 3 rd Appearance  | Interrupt until ANC recovers to $\geq 1 \times 10^9/L$ ; provide growth factor support   | Dose reduce one additional dose level. If dose level 1 at time of AE, discontinue both drugs. |
| 4 th Appearance  | Discontinue Permanently  | N/A   |
|   |  |   |

| Non-Hematologic Related Grade 3 or Grade 4 not related to abnormal liver function (start symptomatic treatment when possible). |   |   |
|---|---|---|
| 1 st Appearance  | Interrupt until recovered (grade 0-1) and provide supportive management | Dose reduce one dose level. If dose level 1 at time of AE, discontinue both drugs.            |

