## **8.2 Phase 2 Dose Modification**

Patients may have dose modifications at any time. Patients may have either drug held for any reason for up to 21 days before discontinuing study treatment. Refer to Tables 10 – 14 below for specific dose modification instructions.

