### 8.2.3 Dose Modification for Non-Hematologic Toxicity

Reduction/interruption of dosing for other AEs may take place at any time. Below are guidelines for dosage modification for Turalio®-related toxicities as well as guidelines for their management. Dose reductions should depend on the toxicity grade, as noted in Table 14. These parameters are only a guide and are not intended to supersede the clinical judgment of the treating physician. All adjustments should be made in consultation with the principal investigator. **Dosing holds longer than 21 days for any reason should generally result in discontinuation from the study**, unless the patient has demonstrated a clinical benefit from therapy and would like to continue dosing with study drug after discussion between the investigator and the Principal investigator.

| Toxicity Grade (CTCAE v4)   | Turalio® and Sirolimus dose changes during current treatment period                      | Dose adjustments for resumption of treatment  |
|---|--|---|
| Hematologic Toxicity   |  |   |
| Any Grade 4, or Grade 3, neutropenia with fever, or thrombocytopenia with bleeding, except for Grade 4 lymphopenia             |  |   |
| 1 st Appearance  | Interrupt until ANC recovers to $\geq 1 \times 10^9/L$ ; growth factor support permitted | Dose reduce Turalio® to 400mg orally in AM and 400mg orally in PM daily.  |
| 2 nd Appearance  | Interrupt until ANC recovers to $\geq 1 \times 10^9/L$ ; provide growth factor support   | If Turalio® total daily dose at 800mg orally, dose reduce Turalio® to 200mg in AM and 400mg in PM. If Sirolimus 2.0mg, decreased to 1.0mg.  |
| 3 rd Appearance  | Interrupt until ANC recovers to $\geq 1 \times 10^9/L$ ; provide growth factor support   | Discontinue study treatments unless subject deriving clinical benefit. Consult with Principal investigator and consider decreasing Turalio® to 200mg twice daily and decrease Sirolimus to half the dose unless at 0.5mg. |
| 4 th Appearance  | Discontinue Permanently  | N/A   |
| Non-Hematologic Related Grade 3 or Grade 4 not related to abnormal liver function (start symptomatic treatment when possible). |  |   |
| 1 st Appearance  | Interrupt until recovered (grade 0-1) and provide supportive management.                 | Dose reduce Turalio® to 400mg orally in AM and 400mg orally in PM daily and Sirolimus to 1.0mg orally in AM.  |

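### Phase 2 uses one hold limit, 21 days, but gives three incompatible rules for what follows a longer toxicity hold; Phase 1 has two limits, 14 days and three weeks

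*Combined protocol and SAP*

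**What the plan says.** **Phase 2.** Section 8.2 sets the general rule: "Patients may have either drug held for any reason for up to 21 days before discontinuing study treatment". It states no exception and names nobody who could grant one.

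Section 8.2.2 deals with interruptions due to toxicity. Those lasting more than 21 "d require treatment discontinuation unless the medical monitor approves continuation". The sentence stands under the hepatotoxicity entry, but its paragraph also refers to hematologic and nonhematologic events.

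Section 8.2.3 says: "Dosing holds longer than 21 days for any reason should generally result in discontinuation from the study". Its exception requires that the patient has shown clinical benefit and would like to "continue dosing with study drug after discussion between the investigator and the Principal investigator". The section opens with this scope: "Reduction/interruption of dosing for other AEs may take place at any time".

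**Phase 1.** Section 8.1 says: "Patients may have drug held for any reason for up to 14 days before discontinuing study treatment". Section 8.1.1.1 uses the same medical-monitor sentence as 8.2.2, with 14 days in place of 21. The text before Table 9 has a different limit: "Dosing interruptions longer than three weeks for any reason should generally result in discontinuation from the study". There the exception again rests on clinical benefit, but the discussion is between the investigator and the sponsor.

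**The concern.** A rule on how long dosing may be interrupted has to give one answer for one patient. Here the answer depends on which subsection the site opens. The sections differ on whether an exception exists, what justifies it, who decides, and whether the patient leaves treatment or the study.

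Two things are at stake. The first is safety oversight. Section 9.1.1 warns that liver injury from Turalio can be severe and prolonged even after the drug is stopped, and may be fatal, so long toxicity holds are foreseeable. Medical-monitor approval appears in one Phase 2 rule and not in the other two.

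The second is consistent conduct in a small trial. Phase 2 plans 25 patients with PFS as the primary endpoint. If sites apply different rules, both exposure after a long hold and possibly follow-up will vary for reasons tied to toxicity.

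**Working it through.** The plan has no figure to reproduce here. The check sets the hold rules side by side.

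**Phase 2, toxicity hold of more than 21 days**

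| Section | Stated scope | Outcome | Exception | Who decides |
|---|---|---|---|---|
| 8.2 | any reason | study treatment ends | none | nobody named |
| 8.2.2 | toxicity | treatment ends | medical monitor approves | medical monitor |
| 8.2.3 | any reason, in a section opening with other AEs | generally, study participation ends | clinical benefit, patient's wish, and discussion | investigator with principal investigator |

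The limit is 21 days in every row, so the length of the hold is not in dispute. Now take a patient whose drugs are held for 25 days for a non-liver toxicity.

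- *Benefit shown, patient wishes to continue, principal investigator consulted, no medical-monitor approval.* 8.2: stop. 8.2.2: stop. 8.2.3: may continue.
- *Medical monitor approves, no clinical benefit shown.* 8.2: stop. 8.2.2: may continue. 8.2.3: generally stop.
- *Both conditions met.* 8.2: stop. 8.2.2 and 8.2.3: may continue.

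The rules give different answers in all three cases. In the first two, 8.2.2 and 8.2.3 point in opposite directions.

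**The same hold for abnormal liver tests.** Section 8.2.3 is headed non-hematologic toxicity, opens with other AEs directly after the hepatotoxicity section, and its Table 14 limits the non-hematologic block to events unrelated to abnormal liver function. It may therefore not reach a liver hold, although its 21-day sentence has no such limit. With 8.2.3 set aside, 8.2 (no exception) and 8.2.2 (medical-monitor exception) still differ. Both hepatotoxicity entries refer to Table 5, which is not in the available text and may carry its own rule. Table 6 adds a restart on recovery in consultation with the principal investigator, with no maximum hold in that row.

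**Phase 1.** Three weeks is 3 × 7 = 21 days. The two limits therefore disagree over 21 − 14 = 7 days, that is, holds of 15 to 21 days.

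| Hold | 8.1 | 8.1.1.1 | Text before Table 9 |
|---|---|---|---|
| 15 to 21 days | treatment ends | ends unless medical monitor approves | limit not reached |
| over 21 days | treatment ends | ends unless medical monitor approves | generally ends study participation, unless clinical benefit and discussion with sponsor |

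**Consequence.** Sections 8.1, 8.1.1.1, 8.2 and 8.2.2 speak of ending treatment. The text before Table 9 and Section 8.2.3 speak of discontinuation from the study. Section 7.4 describes phone contact after removal, to learn about survival and later treatment. Section 4.1 censors patients without progression at their last follow-up. Whether the two phrases mean the same thing therefore bears on tumor assessments and PFS censoring.

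**The case against.** The best defense is that these are a general rule and its specific exceptions. Section 8.2 refers the reader to the tables that follow for specific instructions, so 8.2.2 could govern liver toxicity and 8.2.3 everything else. On that reading much of the conflict disappears, including the difference between 8.2 and 8.2.2 for a liver hold. But the documents do not say this, and the reading needs both subsections to be taken more narrowly than they are worded: 8.2.2 speaks of toxicity in general and 8.2.3 of any reason. The two could also be applied together, with both medical-monitor approval and principal-investigator discussion required. That is workable, but it too is unstated, and it leaves 8.2 with no exception.

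Several stronger readings are tempting and are not supported:

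- *Three competing decision-makers in Phase 2.* Section 8.2 names none. There are two approval routes and one rule without any.
- *A liver hold can escape medical-monitor approval by citing 8.2.3.* Nothing in 8.2.3 waives 8.2.2, and liver holds are where 8.2.3 is least likely to apply. Table 6 also asks that cases be discussed with the principal investigator whenever drug is held for liver tests, and calls for a hepatology consult if values keep rising beyond 14 days.
- *Investigator and principal investigator may be one person, so the 8.2.3 discussion is empty.* No text says so.
- *Patients over the limit lose their scans and their PFS data.* Section 7.5 uses leaving the study and stopping study drug loosely together, and the Schedule of Events is not in the available text. Whether scans stop cannot be determined.

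It is also fair to say that the Phase 1 conflict has little forward effect: Section 13.1 reports 18 evaluable patients already enrolled.

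**Conclusion.** The contradiction is real. In Phase 2 it concerns the exception, the approver and the consequence, not the 21-day limit. It is clearest for non-liver toxicity, where 8.2.2 and 8.2.3 overlap by their own words. For liver holds the firm statement is narrower: 8.2 and 8.2.2 differ as written, subject to whatever Table 5 says.

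In Phase 1, holds of 15 to 21 days have opposite outcomes under the two limits. With enrolment complete, this matters mainly for interpreting the Phase 1 data and for any patient still on treatment.

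The size cannot be given as a count, because the documents do not say how many holds exceed the limits. Each Phase 2 patient handled differently is 1/25 = 4% of the planned sample. An effect on PFS is possible but not shown. The conclusion assumes that no provision outside the available text states which section takes precedence.

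**What to change.** The sponsor should reconcile Sections 8.1, 8.1.1.1, the text before Table 9, 8.2, 8.2.2 and 8.2.3 so that each phase states one hold limit, one exception with one named approver, and one consequence. The rule should stand in one place per phase, and the other sections should refer to it. Table 5 should be checked for agreement at the same time.

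The protocol should also state whether discontinuation from the study and discontinuation of study treatment mean the same thing, and what follows for tumor assessments and PFS censoring. Each exception should be logged with its approver and reason.

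This review does not say which limit, approver or consequence is right. The cost is a wording amendment and a short log, and possibly some loss of local discretion, depending on the approver chosen.

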### 8.2.3 Dose Modification for Non-Hematologic Toxicity

Reduction/interruption of dosing for other AEs may take place at any time. Below are guidelines for dosage modification for Turalio®-related toxicities as well as guidelines for their management. Dose reductions should depend on the toxicity grade, as noted in Table 14. These parameters are only a guide and are not intended to supersede the clinical judgment of the treating physician. All adjustments should be made in consultation with the principal investigator. **Dosing holds longer than 21 days for any reason should generally result in discontinuation from the study**, unless the patient has demonstrated a clinical benefit from therapy and would like to continue dosing with study drug after discussion between the investigator and the Principal investigator.

| Toxicity Grade (CTCAE v4)   | Turalio® and Sirolimus dose changes during current treatment period                      | Dose adjustments for resumption of treatment  |
|---|--|---|
| Hematologic Toxicity   |  |   |
| Any Grade 4, or Grade 3, neutropenia with fever, or thrombocytopenia with bleeding, except for Grade 4 lymphopenia             |  |   |
| 1 st Appearance  | Interrupt until ANC recovers to $\geq 1 \times 10^9/L$ ; growth factor support permitted | Dose reduce Turalio® to 400mg orally in AM and 400mg orally in PM daily.  |
| 2 nd Appearance  | Interrupt until ANC recovers to $\geq 1 \times 10^9/L$ ; provide growth factor support   | If Turalio® total daily dose at 800mg orally, dose reduce Turalio® to 200mg in AM and 400mg in PM. If Sirolimus 2.0mg, decreased to 1.0mg.  |
| 3 rd Appearance  | Interrupt until ANC recovers to $\geq 1 \times 10^9/L$ ; provide growth factor support   | Discontinue study treatments unless subject deriving clinical benefit. Consult with Principal investigator and consider decreasing Turalio® to 200mg twice daily and decrease Sirolimus to half the dose unless at 0.5mg. |
| 4 th Appearance  | Discontinue Permanently  | N/A   |
| Non-Hematologic Related Grade 3 or Grade 4 not related to abnormal liver function (start symptomatic treatment when possible). |  |   |
| 1 st Appearance  | Interrupt until recovered (grade 0-1) and provide supportive management.                 | Dose reduce Turalio® to 400mg orally in AM and 400mg orally in PM daily and Sirolimus to 1.0mg orally in AM.  |
| 2 nd Appearance  | Interrupt until recovered (grade 0-1) and provide supportive management                  | Continue Turalio® at 400mg orally in AM and 400mg orally in PM daily and dose reduce Sirolimus to 0.5mg orally in AM.   |

|                            |   |                               |
|----------------------------|---|-------------------------------|
| 3 rd Appearance | Interrupt until recovered (grade 0-1) and provide supportive management | Discontinue study treatments. |
|----------------------------|---|-------------------------------|

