**Columbia University Medical Center**  
**Herbert Irving Comprehensive Cancer Center**  
**Version Date: 04/21/2021**

receptor antagonist, administer Turalio® at least 2 hours before or 10 hours after taking an H2-receptor antagonist.

Concomitant treatment is permitted if the medication is not expected to interfere with the evaluation of safety or efficacy of the study drug. During the study, if the use of any concomitant treatment becomes necessary (e.g., for treatment of an adverse event), the treatment must be recorded on the eCRF, including the reason for treatment, generic name of the drug, dosage, route, and start and stop dates of administration.

Sirolimus undergoes extensive hepatic and intestinal metabolism via CYP3A4 and CYP3A5, as well as excretion by P-glycoprotein. Strong CYP3A inhibitors such as ketoconazole or grapefruit juice are not permitted. Patients should be monitored for supratherapeutic toxic levels of Sirolimus and Turalio®. As bone marrow suppression including anemia, neutropenia, and thrombocytopenia have been reported in patients receiving Sirolimus monotherapy, these adverse effects may be exacerbated in combination with Turalio® for which patients will be closely monitored.

- 5.2.17. Any patients on warfarin therapy.
- 5.2.18. Hepatobiliary diseases including biliary tract diseases, autoimmune hepatitis, inflammation, fibrosis, cirrhosis of liver caused by viral, alcohol, or genetic reasons. Gilbert's disease is allowed if TBil is  $\leq 1.5 \times$  ULN.

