#### **9.1.2 Sirolimus**

Sirolimus is approved for prophylaxis of organ rejection in patients receiving renal transplants. Known toxicities include risk of opportunistic infections, interstitial lung disease, hyperlipidemia, risk of malignancy (including lymphoma), proteinuria, mucositis, nausea, emesis, diarrhea, edema, elevated liver enzymes, and bone marrow suppression including anemia, neutropenia, and thrombocytopenia.

Side effects that may be seen with Sirolimus given by itself or in combination with other anti-cancer treatments.

Some common side effects ( $\geq 30\%$  by frequency) seen with the use of Sirolimus in patients with cancer include the following:

- Peripheral edema
- Hypertriglyceridemia
- Hypercholesterolemia
- Increased creatinine (kidney dysfunction)
- Hypertension (an increase in blood pressure)
- Nausea
- Abdominal pain
- Diarrhea
- Constipation
- Headache
- Fever
- Urinary tract infection

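### Phase 2 Table 14 ends every hematologic hold on the neutrophil count alone, so an isolated platelet or hemoglobin event has no relevant restart criterion

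*Combined protocol and SAP*

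**What the plan says.** The Phase 2 hematologic rules are in Table 14, in section 8.2.3, although that section's heading names only non-hematologic toxicity. The trigger is "Any Grade 4, or Grade 3, neutropenia with fever, or thrombocytopenia with bleeding, except for Grade 4 lymphopenia". The first, second and third appearance rows each carry the instruction "Interrupt until ANC recovers to" at least 1 × 10^9/L; the fourth is permanent discontinuation. After a first appearance Turalio goes to 800 mg/day and sirolimus is not mentioned. After a second, Turalio goes from 800 to 600 mg/day and sirolimus from 2 to 1 mg. After a third, treatment stops unless the patient is benefiting; in that case 400 mg/day and half the sirolimus dose may be considered.

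The non-hematologic rows of the same table use the event itself as the test: "Interrupt until recovered (grade 0-1) and provide supportive management".

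Two other Phase 2 tables set fixed restart doses. Table 12, for Grade 3 nausea or vomiting that improves within 48 hours, says "then restart at 400mg orally in AM and 400mg orally in PM daily". Table 10, for a first sirolimus trough above 18 µg/L that has fallen by the first recheck, restarts sirolimus at 2 mg.

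Section 8.2 caps holds: "Patients may have either drug held for any reason for up to 21 days before discontinuing study treatment".

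**The concern.** A restart rule should test whether the toxicity that caused the hold has resolved. Table 14 does this for neutropenia but not for the other cell lines in its trigger. In an isolated platelet or hemoglobin event the neutrophil count need not fall, so the stated criterion can be satisfied on the day the hold begins.

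The protocol itself anticipates these toxicities. On giving sirolimus together with Turalio, section 5.2.16 says that "bone marrow suppression including anemia, neutropenia, and thrombocytopenia have been reported in patients receiving Sirolimus monotherapy, these adverse effects may be exacerbated in combination". Section 9.1.2 introduces its list at 30% frequency or more as effects "seen with the use of Sirolimus in patients with cancer include the following", and the list includes anemia and thrombocytopenia. It states no grade, so it shows that these effects are expected but not how often they reach Table 14's trigger.

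The fixed restart doses raise a smaller question: whether a patient already reduced for one toxicity could be moved back up after another. Safety at the recommended dose is a Phase 2 primary objective (section 1.1), so what is at stake is patient protection and consistent handling of toxicity.

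**Working it through.** No sample size or power figure is involved. The check compares trigger with recovery rule, then follows the dose steps.

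**1. What the trigger covers.** Thrombocytopenia with bleeding is named. The comma after the Grade 3 term makes the rest ambiguous; Phase 1 Table 9 has no comma there: "Any Grade 4, or Grade 3 neutropenia with fever, or thrombocytopenia with bleeding and except for Grade 4 lymphopenia". Exempting Grade 4 lymphopenia makes sense only if the Grade 4 limb spans all cell lines, so hemoglobin is covered by inference.

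**2. What ends the hold.** Hematologic rows that interrupt treatment: 3. Rows ending on ANC alone: 3 of 3. Rows naming a platelet or hemoglobin level: 0 of 3. Table 9 uses the same ANC-only recovery rule, so the gap was probably carried over.

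**3. Applied to an isolated platelet or hemoglobin event.** Entry requires ANC of at least 1.5 × 10^9/L (section 5.1.7). If ANC stays at or above 1, the criterion is met at onset and the implied hold is 0 days. If the criterion is treated as inapplicable, only the 21-day limit remains. That range of 0 to 21 days is everything the protocol permits; it is not an estimate. After a first event a patient on sirolimus 2 mg resumes at 2 mg.

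**4. What other rows catch.** A Grade 3 or 4 bleed would also fall under the non-hematologic rows and be held to grade 0-1. The gap is therefore the blood count itself and lower-grade bleeding.

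**5. Fixed restart doses.** The Phase 2 starting dose is Turalio 1000 mg/day with sirolimus 2 mg (section 9.6.1). Table 12 restarts Turalio at 400 + 400 = 800 mg/day.

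| Rule | Dose before hold | Restart | Ratio | Change |
|---|---|---|---|---|
| Table 12, Turalio | 1000 mg | 800 mg | 800/1000 = 0.80 | -20% |
| Table 12, Turalio | 800 mg | 800 mg | 800/800 = 1.00 | 0% |
| Table 12, Turalio | 600 mg | 800 mg | 800/600 = 1.33 | +33% |
| Table 12, Turalio | 400 mg | 800 mg | 800/400 = 2.00 | +100% |
| Table 10 first event, sirolimus | 2 mg | 2 mg | 2/2 = 1.00 | 0% |
| Table 10 first event, sirolimus | 1 mg | 2 mg | 2/1 = 2.00 | +100% |

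Through Table 14, reaching 600 mg needs two hematologic events; reaching 400 mg needs a third with treatment continued. Sirolimus is at 1 mg before any high trough only after a second hematologic event, a first non-hematologic event, or a Grade 3 hyperglycemia hold of more than 7 days (Table 13). From the starting dose, no step raises either drug.

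**6. Phase 1 comparison.** Table 7 restarted Turalio at the next lower cohort dose, and Table 4 restarted sirolimus at its original dose after a first event. Neither could raise a dose. Table 14's second hematologic row is likewise conditional on the current Turalio dose, so conditional wording was available.

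**The case against.** The strongest reply is that these tables do not operate alone. Section 8.2.3 calls its parameters guidance that does not override clinical judgment, and requires every adjustment to be made in consultation with the principal investigator. Section 8.2.2 lets the investigator interrupt dosing for any clinically significant toxicity. Section 8.2.1 allows departures from Table 10 after discussion with the principal investigator. Tables 10, 12 and 14 are captioned as recommendations.

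This stands against two stronger readings. A reader might infer that Table 14 compels a restart during ongoing severe thrombocytopenia. It does not, because a hold may continue at discretion within the 21-day limit. A reader might also infer that each physician chooses the restart point alone. That is not so either, because the principal investigator must be consulted. What remains is that none of these provisions states a platelet or hemoglobin criterion.

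On the fixed doses, the governing text of sections 8.2.1 to 8.2.3 speaks of holding, interrupting or reducing, which points away from re-escalation. The sirolimus path also needs a first high trough at half dose, although four troughs are scheduled in Cycle 1. Both arguments make these paths rare and unintended; they do not change what the cells say. A reader might go further and infer a fourfold rise in sirolimus from 0.5 to 2 mg. That requires confining Table 10's instruction to discontinue at 0.5 mg to third and later events, which its wording does not require.

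**Conclusion.** The concern holds as a minor safety-drafting point. The main part is that 3 of 3 hematologic hold rows in Phase 2 Table 14 end on ANC alone, although the trigger reaches platelets expressly and hemoglobin by inference. For an isolated event in either line the stated rule is already met or irrelevant. The secondary part is that, on rare paths and read literally, Table 12 can raise Turalio by 33% or 100%, and Table 10 can raise sirolimus by 100%, contrary to the evident intent of section 8.2.1.

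The documents do not support putting a probability on a premature restart. They give no rate for qualifying platelet or hemoglobin events or for the fixed-dose paths, and a qualifying event is not itself a premature restart. Nor do they support any effect on PFS, power or the analysis.

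The conclusion assumes that no general recovery rule appears in text not available for this review, which includes Tables 5 and 11, the text between sections 5.2.18 and 7.3, sections 9.2 to 9.5, and sections 10 and 12. Such a rule cannot be excluded, so confidence is medium.

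**What to change.** Amend the Phase 2 tables as follows.

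1. In Table 14's hematologic rows, end the hold on recovery of the cell line that triggered it (ANC, platelets or hemoglobin) and on resolution of any bleeding. The sponsor should set the thresholds; the documents give none to propose.
2. In Tables 10 and 12, restart at the listed dose or the pre-event dose, whichever is lower. By construction this removes every increase shown above.

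The same whichever-is-lower wording in Table 13 and in Table 14's non-hematologic rows is an optional conforming edit, since those rows already speak of reducing or continuing. Correcting the comma in Table 14's trigger would be sensible at the same time. Table 9 needs no change unless Phase 1 patients are still on treatment, because Phase 1 enrollment is complete (section 13.1).

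The cost is a text amendment, with no added patients, visits or procedures.
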